1. **Randomization assignment:** As previously noted randomization will be 1:1 for nicotine inhaler or placebo assignment. To ensure comparability of subjects in the treatment groups, we will employ urn randomization, a probabilistic balancing procedure that assigns patients to conditions so that groups are balanced on key variables [57]. Key variables that we would like to balance groups on include history of preterm delivery (yes/no), gestational age at study entry (<19 weeks vs. \geq 19 weeks), and number of CPD (<10 vs. \geq 10).

The nurse will fax key variables for a given subject to the research pharmacist at UCONN who will enter these variables into a specially developed computer algorithm by that is

the basis for the urn randomization procedure. In this way, treatment groups will be comparable on important features that may influence treatment outcome. Once the pharmacist enters these variables, the computer assigns a treatment assignment. The pharmacist will communicate with the study nurse (by fax or e-mail) which medication box # to dispense to the subject.

2. **Maternal blood draw** (approximately 15 cc): Venipuncture will be performed using standard sterile blood drawing techniques by trained personnel. Serum will be separated on site and stored at -20 degrees C on at least a biweekly basis until transfer to UCHC where it will be stored at -70 C. Samples will be measured for cotinine, the major metabolite of nicotine, and a reliable measure of overall nicotine intake. Cotinine will be measured by GC/Mass Spectrometry at Yale University. UCHC Core Lab will ship transport tubes to Yale after subjects' Week 2 visit. If the subject does not come to Visit 2, the blood will be obtained at the next scheduled visit. Serum will also be measured for hydroxycotinine/cotinine ratio, the rate at which nicotine is metabolized. Samples will be shipped in compliance with DOT/IATA regulations (dry ice, Fed-Ex Overnight Express, etc.). The results will be emailed to the P.I. and the study coordinator at each site. Serum will measured for high sensitivity C-reactive protein (Siemens Medical Diagnostics, Los Angeles CA) by solid phase chemiluminescent immunometric assay and sICAM (R&D systems, Minneapolis, MN) measured by sandwich EIA in the GCRC core laboratory. If possible, this blood draw will be incorporated with other routine prenatal blood draws.
3. **Urine sample:** Urine will only be used as a backup for cotinine if necessary.

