Describe length of subject's participation in the study including number of visits, frequency of visits, and length of visits:

The subject will be in the study from the time of enrollment (13-26 weeks gestation) until 6 months after delivery. Each subject will have 10 visits. The screen and baseline visit are each 1.5 hours long. The remaining visits are approximately 45 minutes long.

Methods of Data Collection and Types of Data to be collected (may refer to attached surveys/ forms etc.)
See Attached surveys

Method(s) of data analysis:

Specific Aim 1: To compare the efficacy in pregnant smokers of the nicotine inhaler or matching placebo for smoking cessation and reduction in pregnant smokers We will first examine variation in the main outcome (7 day PPA rates at 32-34 weeks gestation) by treatment site using the intraclass correlation coefficient. If there is a difference by site, it will be used as a nesting factor in a generalized estimating equations logistic model. At the end of patient follow-up, the difference in the proportion of subjects who successfully quit smoking will be calculated along with a 95% confidence interval for the “true” difference between treatment groups. To evaluate whether randomization was effective, summary statistics for patient characteristics in the two study arms will be compared. If there is an imbalance in patient characteristics, statistical adjustment will be used to ensure that the initial results were not biased by those imbalances.

We will use a linear mixed model to evaluate the effects of the nicotine inhaler on smoking reduction or exhaled CO from baseline first to 6 weeks and then to 32 weeks gestation. Prior to these analyses, the distribution of the dependent variables, number of CPD (and exhaled CO), will be examined for normality and outliers and transformations will be performed if necessary. Treatment group and visit will be fixed factors and the intercept will be random. The model will also include a treatment-by-time interaction to test whether, over time, the number of CPD changes differentially by treatment group.

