Specific Aim 2.a: To compare effects of the nicotine inhaler with placebo on overall nicotine exposure (i.e., measured as serum cotinine), and birth outcomes [i.e., birth weight, gestational age, % of subjects who deliver a LBW (<2500 g) or preterm (<37 wk gestation) infant]. We will use a linear mixed model (see above) to determine whether cotinine concentration changes differentially over time by treatment group.

Specific Aim 2.b: Birth Outcomes. Mean birth weight will be compared for treatment groups using a two-sample t-test, or analysis of covariance if necessary to adjust for imbalances in patient characteristics. We will also compare the percentage of subjects in each group who deliver an infant of LBW (1500-2500 g) or preterm delivery using chi square or logistical regression.

Specific Aim 3: To determine which subjects benefit most from NRT, we will use logistic regression to examine the following predictors of treatment response (i.e., smoking cessation at 6 or 32 wks

Nicotine Replacement for Smoking Cessation during Pregnancy

gestation): pretreatment CPD, FTND score, perceived stress, motivation to quit, self-efficacy, treatment group, and the interaction of treatment group and the other independent (i.e., potential moderator) variables. **Analyses:** First, we will use a stepwise procedure to choose predictor variables and interaction terms that are significant ($\alpha=0.05$). A significant interaction between treatment group and other variables (e.g., pretreatment CPD) implies that the regression coefficients for this variable are not homogeneous with respect to the efficacy of the medication. The Johnson-Neyman procedure [79], which yields values of the continuous moderator variable at which the treatment groups differ significantly on the dependent variable, will be used to determine the “break point” nicotine inhaler efficacy. In our completed study[1], the effect of nicotine gum appeared to depend on CPD during the pretreatment period. For light smokers, the cessation rates were 18% and 21% for the control and nicotine groups, respectively, while for heavy smokers the rates were 0% and 15%, respectively. Since a similar effect in a sample of 150 women would provide power=0.80, using a two-sided $\alpha=0.05$, our proposed sample of 360 pregnant smokers will provide more than adequate power to detect the effect.

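### The trial balances allocation on three prognostic factors by urn, but the abstinence and birth-weight comparisons leave them out and admit covariates only if an imbalance is seen: a modest, avoidable loss of precision and an open choice of definitive result

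*Combined protocol and SAP*

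**What the plan says.** **Allocation** (Study Procedures, Baseline, item 1, Randomization assignment): "we will employ urn randomization, a probabilistic balancing procedure that assigns patients to conditions so that groups are balanced on key variables". The factors are listed as follows: "Key variables that we would like to balance groups on include history of preterm delivery (yes/no), gestational age at study entry" (under 19 weeks against 19 or more), and CPD (under 10 against 10 or more). The reason given is that such features could affect outcome.

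**Abstinence** (Method(s) of data analysis, Specific Aim 1): the analysis begins by examining "variation in the main outcome (7 day PPA rates at 32-34 weeks gestation) by treatment site". On site it says: "If there is a difference by site, it will be used as a nesting factor in a generalized estimating equations logistic model". For the treatment comparison, "the difference in the proportion of subjects who successfully quit smoking will be calculated along with a 95% confidence interval". The arms are then compared on patient characteristics, and "If there is an imbalance in patient characteristics, statistical adjustment will be used to ensure that the initial results were not biased" by those imbalances.

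**Birth outcomes** (Specific Aim 2.b): mean birth weight is compared "using a two-sample t-test, or analysis of covariance if necessary to adjust for imbalances in patient characteristics". Low birth weight and preterm delivery get a chi-square test or logistic regression, with no rule for choosing. No test is named there for mean gestational age.

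No urn factor is named in these comparisons. No imbalance criterion, covariate list or adjusted model is given. CPD appears as a predictor only in the Specific Aim 3 moderator model, where stepwise selection decides whether it stays.

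**The concern.** A design that forces balance on prognostic factors makes the treatment estimate less variable. An analysis that leaves those factors out does not credit that reduction: its standard error is somewhat too large and its test slightly conservative.

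The imbalance trigger does not repair this. It selects on observed difference between arms rather than on prognosis, and the urn suppresses differences in exactly the variables the sponsor thought prognostic.

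The documents' own evidence says the factors matter. Sample size and justification, Aim 3, reports control quit rates of 18% in light and 0% in heavy smokers. Section A.1 gives 20%, 15% and 5% by rising CPD band. Section A.2.a describes a nicotine replacement trial whose serious-adverse-event difference was not significant (p=0.09) after adjustment for preterm history.

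At stake are some precision and a clear statement of which result counts.

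**Working it through.** **1. The plan's own figure.** Inputs (Sample size and justification, Aim 1): 14.9% and 26.9%, two-sided alpha 0.05, power 0.80. With the pooled-variance formula and no continuity correction, the mean rate is 0.209 and

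n per arm = [1.96 × √(2 × 0.209 × 0.791) + 0.8416 × √(0.149 × 0.851 + 0.269 × 0.731)]² / 0.12² = (1.127 + 0.479)² / 0.0144 ≈ 179, i.e. 180 with rounding.

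Power at 180 per arm is 0.802. The stated 360 is therefore the covariate-free test, and it reproduces.

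**2. What the trigger admits.** The plan states no criterion; assume p<0.05 per characteristic. I simulated urn allocation of 360 women with the three urn factors plus five other covariates (3,000 trials per scenario). Adjustment was triggered in 22–24% of trials. Five independent covariates alone would give 1 − 0.95⁵ = 22.6%. The urn factors thus contribute almost nothing to the trigger.

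**3. Abstinence, direct calculation.** Take the four Aim 3 rates (light 18% control, 21% nicotine; heavy 0%, 15%) and assume 40% heavy smokers.

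- Control: 0.6 × 0.18 = 0.108. Nicotine: 0.6 × 0.21 + 0.4 × 0.15 = 0.186. Difference 0.078.
- Unadjusted SE = √[(0.108 × 0.892 + 0.186 × 0.814)/180] = 0.0371.
- Stratified SE = √[(0.6 × 0.18 × 0.82 + 0.6 × 0.21 × 0.79 + 0.4 × 0.15 × 0.85)/180] = 0.0364.
- The unadjusted SE is about 1.8% too large. Power is Φ(0.078/0.0371 − 1.96) ≈ 0.56, against about 0.57 stratified.

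**4. Abstinence, simulation.** Odds ratio 2.1 as in Aim 1, 360 women, CPD balanced, chi-square against Cochran-Mantel-Haenszel on CPD, 20,000 trials per scenario (simulation error about 0.3 points on power). The heavy shares of 17% and 34% are those that give 14.9% overall: 1 − 0.149/0.18 = 0.172, and (0.20 − 0.149)/0.15 = 0.34. The 40% and 50% shares are assumed.

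| Placebo quit rate, light / heavy | Heavy share | Power, unadjusted → stratified | Type I error, unadjusted → stratified |
|---|---|---|---|
| 18% / about 0% | 17% | 0.769 → 0.781 | 0.048 → 0.053 |
| 20% / 5% | 34% | 0.766 → 0.781 | 0.043 → 0.047 |
| 20% / 15% | 50% | 0.846 → 0.847 | 0.049 → 0.050 |
| 18% / about 0% | 40% | 0.598 → 0.640 | 0.042 → 0.051 |

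In the urn simulation with assumed factor odds ratios of 0.5, 0.5 and 0.25, power was 0.714 unadjusted, 0.715 when adjusting only on imbalance, and 0.741 with prespecified adjustment (simulation error 0.7–0.8 points). The conditional rule recovered essentially none of the available gain.

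**5. Type I error of the conditional rule.** Across the urn simulations for abstinence and birth weight it was 0.044–0.055, against 0.046–0.057 unadjusted. Simulation error is √(0.05 × 0.95/3000) = 0.004. There is no material inflation.

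**6. Birth weight.** Inputs (Aim 2): 300 g, SD 607 g. The SE of the difference is 607 × √(2/180) = 64.0 g. Power for 300 g is Φ(300/64.0 − 1.96) = 0.997. The difference detectable at 80% power is 2.80 × 64.0 ≈ 179 g. Adjustment multiplies it by √(1 − R²): 176 g at R² = 0.04, 171 g at 0.09, 164 g at 0.16. These R² values are assumptions.

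**The case against.** An unadjusted comparison after balanced allocation is valid and at worst slightly conservative, and the sample size was built on it. That stands in full.

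The Aim 1 wording can be read as fixing the unadjusted difference as the result, with adjustment only as a check on it. A reader might infer that chance baseline differences choose the primary model; for abstinence the text does not go that far. But this reading still leaves the urn factors out of the main analysis, and it does not cover Specific Aim 2.b, where "two-sample t-test, or analysis of covariance if necessary to adjust for imbalances in patient characteristics" offers two alternatives.

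A reader might also infer that formal baseline tests drive the choice. With 15 independent characteristics tested at p<0.05, at least one would be flagged in 1 − 0.95¹⁵ = 54% of trials. The plan speaks only of comparing summary statistics. It gives neither a p-value rule nor a count, so that figure illustrates an assumed rule.

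A larger precision loss is tempting too: an SE about 5% too large (0.0423 against 0.0402). This needs about 25% quitting among light placebo smokers and a constant 12-point effect. The Aim 3 rates are 18%, with effects of 3 points in light and 15 points in heavy smokers, and they give the 1.8% shown above.

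Finally, the urn factors are not ignored altogether. CPD is examined in Aim 3, and any factor could enter through the imbalance clause. Neither makes it part of the prespecified main comparison.

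**Conclusion.** The point holds as a matter of efficiency and prespecification. The factors that govern allocation are absent from the abstinence and birth-weight comparisons, the trigger for adjustment is unlikely to bring them in, and the plan does not say which result is definitive. Site is a second term whose entry depends on the data, with no threshold.

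The cost is modest: about 0 to 4 power points for abstinence, and a test whose type I error falls to about 0.042 in the most conservative scenario. For birth weight the loss is negligible at the planned 300 g and amounts to 3–15 g in the detectable difference over the assumed R² range. These sizes rest on the assumed heavy-smoker share, the prognostic strength of CPD and the other factors, and an assumed p<0.05 trigger.

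Nothing here shows bias or inflated type I error, and 360 women at power 0.80 stands. With 0.802 power under the planned test, a gain that costs nothing is still worth taking.

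**What to change.** Prespecify as primary one model per outcome with treatment, the three urn factors and site:

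- **Abstinence:** logistic regression, reporting the standardised risk difference with a 95% confidence interval (delta-method or robust variance).
- **Birth weight and gestational age:** analysis of covariance. This also supplies the missing test for gestational age.
- **Low birth weight and preterm delivery:** logistic regression.

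Report the unadjusted result as supportive, keep the baseline table descriptive, and delete the imbalance trigger in Specific Aim 1 and the conditional wording in Specific Aim 2.b. State how site is coded, since Baystate visits may take place at several practices.

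The planned rates imply 180 × (0.149 + 0.269) ≈ 75 quitters. With site coded as two levels, that is about 15 for each of five coefficients, enough for this model. The cost is a few sentences of analysis text: all the variables are already collected, and the sample size does not change.

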Visits 7 & 8: 1- and 6-month postpartum follow-up visits will be completed to assess smoking relapse. We have chosen these time points because the majority of post-partum relapses occur during this period [18]. To reduce subject burden visit 7 will be done by phone. If unable to contact participant, the chart will be reviewed for smoking status.

Visit 7 (1 month postpartum +/- 7 days). The following items will be assessed by research nurse or study coordinator via a telephone call. Nicotine Use survey

1. Counseling to encourage abstinence postpartum

Visit 8 (approximately 6 months postpartum +/- 14 days). The following items will be assessed by research nurse or study coordinator.

1. Nicotine Use survey
2. Exhaled CO measurement if visit is attended
3. Counseling to encourage abstinence postpartum

As a back-up plan, study staff (not R.N.) will perform study procedures at visits that do not require study drug dispensement (Visits 1, 3, and 6). In this instance, the R.N. will complete the behavioral counseling via the telephone.

Sample size and justification:

Aim 1: Based on our nicotine gum study, we estimate that the quit rate will be 14.9% in the placebo group and 26.9% in the nicotine inhaler group (consistent with an odds ratio of 2.1 obtained in meta-analyses of inhaler effects in non-pregnant smokers [2]. Thus, 360 women (180 in each of the treatment group) would yield power of 0.80 to detect a significant difference using a two-tailed test and $\alpha=0.05$. Thus, 360 women (180 in each of the treatment group) would yield power of 0.80 to detect a significant difference using a two-tailed test and $\alpha=0.05$.

Nicotine Replacement for Smoking Cessation during Pregnancy

Aim 2: Using data from our completed study, a total of 226 subjects will yield power=0.80 (two-sided $\alpha=0.05$) to detect a difference of 100 ng/mL (SD=360) in the reduction in cotinine concentrations between groups. In our completed study (N=194), we observed a difference in birth weight of approximately 300 grams (SD 607), which was highly significant. Assuming a comparable effect size, we will have more than adequate power to detect birth weight differences between groups. Thus, our sample size of 360 is more than sufficient for this aim.

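### The mixed model for CPD, exhaled CO and cotinine does not say how the baseline value enters; as most naturally read, it gives up precision that baseline adjustment would recover at no cost.

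*Combined protocol and SAP*

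**What the plan says.** Under Method(s) of data analysis, Specific Aim 1, a linear mixed model evaluates the inhaler's effect "on smoking reduction or exhaled CO from baseline first to 6 weeks and then to 32 weeks gestation". The responses are the measurements themselves, not change scores: "the distribution of the dependent variables, number of CPD (and exhaled CO), will be examined for normality and outliers". The structure is "Treatment group and visit will be fixed factors and the intercept will be random". The treatment effect is carried by an interaction: "The model will also include a treatment-by-time interaction to test whether, over time, the number of CPD changes differentially by treatment group".

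Specific Aim 2.a takes the same model over for cotinine: "We will use a linear mixed model (see above) to determine whether cotinine concentration changes differentially over time by treatment group".

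Adjustment appears only in conditional form, in the preceding paragraph, which deals with the abstinence comparison: "If there is an imbalance in patient characteristics, statistical adjustment will be used". Nothing in either place names the baseline value as a covariate or requires both arms to share one baseline mean.

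The only power figure for an outcome analysed this way is in Sample size and justification, Aim 2: "a total of 226 subjects will yield power=0.80" (two-sided α = 0.05) "to detect a difference of 100 ng/mL (SD=360) in the reduction in cotinine concentrations between groups".

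**The concern.** A change from baseline can be tested by a treatment-by-time interaction only if baseline is among the responses. So the natural reading has baseline as one level of visit. With a treatment main effect also in the model, the arms are then free to differ at baseline. Women are allocated 1:1 before treatment, so any baseline difference is chance. Estimating it as a free parameter and subtracting it adds noise to every later contrast.

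Precision is what is at stake. CPD reduction is part of Hypothesis 1, and cotinine is a stated safety measure under Aim 2. These comparisons may be less sharp than the collected data allow, and more exposed to a chance baseline difference than they need to be.

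**Working it through.** **Inputs from the documents.** 1:1 allocation, 180 per arm. Cotinine difference 100 ng/mL, SD 360, two-sided α = 0.05, power 0.80, total 226 (Sample size, Aim 2). Data collected from 75% of subjects in the investigators' completed gum trial (Incentives paragraph).

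**Not in the documents, so assumed.** The correlation ρ between baseline and follow-up values, taken as 0.3 to 0.7, and the SDs at baseline (s0) and follow-up (s1).

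**1. The plan's own figure.** Reading 360 as the SD of the reduction:

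n per arm = 2 × (1.960 + 0.842)² × 360² / 100² = 2 × 7.849 × 12.96 = 203.4, so 204 per arm and 408 in total.

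The stated 226 does not reproduce. On this reading power is 0.55 with 226 women and 0.75 with 360. A total of 226 needs an SD of about 268. That would follow if 360 were the SD of a single cotinine value and ρ about 0.72, since 360 × √(2 × 0.28) ≈ 269, but the documents do not say so. The meaning of SD 360 is therefore open, and steps 2 to 5 do not use it.

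**2. What the interaction estimates.** With complete data, the coefficient at visit j is (active mean at j − active mean at baseline) − (placebo mean at j − placebo mean at baseline), the difference in mean change. An exact generalised least squares calculation under a random intercept, for 2, 3, 4, 6 and 7 visits, gave a standard error equal to that of the change-score difference each time (ratio 1.000).

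**3. Equal SDs, complete data.** Per-woman variance is 2σ²(1 − ρ) for change and σ²(1 − ρ²) after baseline adjustment. The ratio adjusted/change is (1 + ρ)/2, so the variance loss is (1 − ρ)/2 and the standard-error loss is 1 − √((1 + ρ)/2).

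| ρ | adjusted / change variance | variance loss | SE loss |
|---|---|---|---|
| 0.3 | 0.65 | 35% | 19% |
| 0.5 | 0.75 | 25% | 13% |
| 0.7 | 0.85 | 15% | 8% |
| 0.9 | 0.95 | 5% | 2.5% |

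**4. A quarter of women missing the last visit.** With the same calculation and all earlier visits present, the common-baseline model has 0.705–0.712 of the variance at ρ = 0.3, 0.79–0.80 at 0.5 and 0.874–0.883 at 0.7. The loss is about 29%, 20–21% and 12–13%. The mixed-model contrast is then no longer the completers' change score; its variance is about 4% to 11% smaller than that.

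**5. Unequal SDs.** With k = s0/s1, the complete-data loss is (k − ρ)² / (1 + k² − 2kρ).

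- k = 0.8: ρ = 0.3 gives 0.25/1.16 = 22%; ρ = 0.7 gives 0.01/0.52 = 2%.
- k = 1.25: ρ = 0.3 gives 0.9025/1.8125 = 50%; ρ = 0.7 gives 0.3025/0.8125 = 37%.
- The loss is zero when k = ρ and never negative.

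**6. Cotinine power, conditional only.** If 360 is the SD of the reduction, SDs are equal and all 180 per arm contribute, a change comparison has power 0.75. Baseline adjustment has residual SD 360 × √((1 + ρ)/2) = 290, 312 or 332 and power 0.905, 0.86 or 0.815 at ρ = 0.3, 0.5 or 0.7. If instead 360 is a single-value SD with ρ about 0.72, the two powers are 0.94 and 0.97.

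**The case against.** **The plan never says baseline is a response row.** True. That is an inference from the model running from baseline, the group main effect and the interaction. If the sponsor meant something else, the plan is silent on how baseline enters, and the same clarification is needed.

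**A reader might infer that 15–35% is a property of this trial.** The documents do not support that. It is (1 − ρ)/2 for assumed correlations, with equal SDs and complete data. For CPD, equal SDs cannot be presumed: women enter at 5 or more a day and quitters go to zero.

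**A reader might infer a definite rise in cotinine power, such as 0.75 to 0.90.** That depends on a reading of SD 360 under which the plan's own 226 fails. On another reading the gain is 0.03. The power figures cannot carry the argument.

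**Safeguards exist.** Urn randomisation balances CPD, but only as below 10 versus 10 or more, and it does not cover CO or cotinine. It may make the real gain for CPD smaller than the formula gives. Adjustment if imbalance is observed is a data-dependent step written beside the abstinence analysis; it is not a pre-specified baseline term.

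**The plan tests the interaction over visits and names no single-visit contrast.** Correct, but a joint test does not remove the loss. Under compound symmetry, complete data and a constant effect over m post-baseline visits, the noncentrality ratio in favour of adjustment is (1 + m)/(1 + mρ). For three post-baseline cotinine samples, if all are assayed, that is 4/1.9 = 2.1, 4/2.5 = 1.6 and 4/3.1 = 1.29 at ρ = 0.3, 0.5 and 0.7.

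**The model is valid and widely used.** This stands. It is unbiased under randomisation and keeps its type I error.

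**Conclusion.** The point holds as a free gain in efficiency, resting on the most natural reading of the model. On that reading each complete-data visit contrast is a change-score difference, which in large samples is never more precise than a baseline-adjusted analysis of the same data.

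The size cannot be derived from the documents. For equal SDs and ρ of 0.3 to 0.7 the variance loss is 35% to 15% with complete data and about 29% to 12% with a quarter missing the last visit. For SD ratios of 0.8 to 1.25 the complete-data loss runs from near zero to about 50%.

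A reader might infer that the comparisons are biased, that false positives are inflated, or that the trial's main result is weakened. None of these follows. Only CPD, exhaled CO and cotinine are affected; 7-day abstinence at 32–34 weeks is analysed separately. Nor does it follow that every comparison must lose precision, because the loss vanishes when the SD ratio equals the correlation.

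**What to change.** In Specific Aim 1 (mixed model) and Specific Aim 2.a, state one of the following for CPD, exhaled CO and cotinine, for both the 6-week and the 32-week analyses:

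- the baseline value is a covariate, its slope allowed to vary by visit, and only post-baseline visits are responses; or
- baseline stays as a response with one mean common to both arms. This means no treatment main effect, treatment terms at post-baseline visits only, and a covariance that does not force equal variances.

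Say that this applies whether or not an imbalance is observed, and name the visit contrast or joint test that answers each hypothesis.

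The cost is a sentence or two of analysis wording, settled before unblinding. The baseline values are already collected, so no new data, visits or women are needed. Separately, the Aim 2 sample-size paragraph should say what SD 360 refers to, since 226 does not follow if it is the SD of the reduction.
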